The **Anchorsure**® (Figure 2 and Figure 3) is a new FDA-approved sacrospinous ligament fixation device that deploys a permanent anchor directly into the ligament and requires high pull-out force for extraction. The device is a Class II surgical device that was FDA approved via a 510(k) premarket notification in 2012. Its approval was based on the FDA approved device Surelift® (Neomedic). Surelift® uses the same anchoring system as Anchorsure but is attached to vaginal mesh as opposed to Anchorsure which is designed to attach to suture material. Surelift® is used widely and has been studied in abstracts⁵⁻⁹ and a published study¹⁰ confirming safety and surgical efficacy. Abstracts on the use of Anchorsure have additionally been published indicating safety and efficacy of use.^{11,12} A summary of the available data for the Capio Slim[™], Surelift®, and Anchorsure® devices is listed in Appendix 1.

The **primary aim** of this study is to conduct a prospective randomized trial of this new anchor-based system versus our current suture-capture-based fixation systems to compare the rates of postoperative buttock and posterior thigh pain. This is important because decreased buttock and posterior thigh pain can reduce patient suffering and potentially reduce postop narcotic use. Our **secondary aims** are to compare intraoperative complications, general postoperative pelvic pain and post-hospitalization opioid use as well as surgeon satisfaction and surgical efficiency with the device. The demonstration of a significant decrease in postoperative buttock or thigh pain, improved surgeon efficiency, or decreased operative time with the use of the Anchorsure device will demonstrate an advantage of the suture anchoring devices over suture capture devices and will fuel the need for a larger efficacy study for the Anchorsure device. Demonstration of improved safety and/or improved surgical outcomes could ultimately change the standard in sacrospinous ligament fixation surgical technique.

[figure not shown]
[figure not shown]

Figure 2. Anchorsure® System¹³

[figure not shown]

Figure 3. Anchorsure® System application to sacrospinous ligament¹³

STUDY OBJECTIVES

Hypothesis 1: Anchorsure® System will reduce postoperative buttock and posterior thigh pain at 1 day, 1 week, and 6 weeks following sacrospinous ligament fixation compared to the Capio[™] Slim Suture Capturing Device

Specific Aim 1:

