To conduct a prospective, randomized, single-blind trial of sacrospinous ligament fixation of the cervix or vaginal apex using Anchorsure® system versus the CapioTM Slim device in women with \geq Stage II pelvic organ prolapse who are undergoing native tissue vaginal repair. The **primary outcome** will be the level of postoperative pain using a 10-point numerical rating scale (NRS) on postoperative day 1, week 1, and 6 weeks postoperatively for pain that is localized to the posterior thigh or buttocks on the side(s) that the sacrospinous fixation was performed. The difference in mean pain ratings will be at least 2.5 on the 10-point NRS.

Hypothesis 2: Surgeon satisfaction, surgical efficiency, intraoperative complications, objective surgical success, symptomatic success, opioid use within the first week postoperatively following hospitalization, and overall postoperative pelvic pain will be similar for both devices.

Specific Aim 2:

The **secondary outcomes** will compare overall surgeon satisfaction with the 2 devices using a 5-point Likert rating scale and surgical efficiency measured in minutes from the start of the use of the surgical device until the surgeon is satisfied with the application of all sacrospinous sutures (does not require the sutures to be tied down). Intraoperative complication related to sacrospinous ligament suspension will be recorded including the need for suture or anchor replacement, hemorrhage that requires additional surgical interventions or blood transfusion, and equipment malfunction. General postoperative pelvic pain will be assessed at postoperative day 1, week 1, and 6 weeks along with buttock and posterior thigh pain via NRS questionnaires. Objective apical repair anatomical success will be assessed at the 6 week postoperative visit via a POP-Q examination with Stage II or greater indicating anatomical failure. Symptomatic surgical success will be evaluated by statistically significant increases or decreases in the responses to the PFDI-20 and PFIQ-7 questionnaires at the 6 week postoperative values.

SUBJECT SELECTION

Inclusion Criteria

- 1. Female patients
- 2. At least 21 years of age
- 3. Surgical plan that includes a native tissue vaginal repair with apical support via sacrospinous ligament fixation. We will permit both hysteropexy and post-hysterectomy sacrospinous ligament suspension
- 4. Understanding and acceptance of the need to return for the 6 week followup visit

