This trial has a **primary** outcome of level of postoperative buttock or posterior thigh pain on postoperative day 1, week1, and 6 weeks as measured using the NRS. An independent t-test will be used to compare the means of the NRS scores from the two groups. The NRS is one of the most common validated pain questionnaire modalities.^{17,18,19,20,21} A clinically significant difference will be considered 2.5 on the 10-point NRS based on a prior paper assessing buttock pain from sacrospinous ligament fixation²² and with published studies assessing clinically meaningful decreases in acute pain.^{18,17} The patient's will be given copies of the NRS questionnaire which will be collected in person on postoperative day 1, week 1, and 6 weeks postoperatively.

Secondary outcome measures will assess the degree to which the study intervention influences surgeon satisfaction, surgical efficiency, adverse events intra- and postoperatively, surgical success, symptomatic success, and the level of postoperative general pelvic pain. Surgeon satisfaction will be assessed via a 5-point rating scale (very dissatisfied, somewhat dissatisfied, neutral, satisfied, very satisfied) and treated as categorical values. Surgical efficiency will be assessed as continuous data measured as a means in minutes. Adverse events will be evaluated as dichotomous data. All adverse events will be reported by the Dindo classification system. Short-term objective surgical success will be assessed by a postoperative exam at 6 weeks and descent of the vaginal apex beyond TVL/2 will be considered surgical failure. Symptomatic success will be assessed by the PDFI-20 guestionnaires to be given at 6-weeks post-operation and compared to preoperative values. The patient's will also be queried about their general pelvic pain on the same questionnaires used to assess buttock and posterior thigh pain. Oral opioid use following hospitalization until postoperation day 6 will be recorded via opioid use questions on the 1 week postoperation guestionnaire. The opioid dose will be converted into morphine equivalents for data analysis. Statistical analysis will be done in collaboration with the Wake Forest Baptist Hospital CTSI Biostatistics Department. Independent t-tests will be used for all continuous data, except for the PFDI and PFIQ data that will use paired t-tests as the two samples are dependent. Chi-square tests will be used for all dichotomous and categorical data.

POWER CALCULATION:

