This study is a head to head two sample comparative study. The null hypothesis is that there is no difference in the prevalence of immediate postoperative new buttock or posterior thigh pain with the use of the Anchorsure® System compared to the Capio[™] Slim device for sacrospinous ligament fixation. In prior published study by Ferrando et al the mean postoperative day 1 buttock or posterior thigh pain had a greater standard deviation (2.7-2.9) compared to week

1 and week 6 data. Therefore for our power calculation used an expected standard deviation of 2.9 to provide confidence in our power of assessing the difference in pain scores across all three timepoints.²² A decrease in in-hospital postoperative buttock or posterior thigh pain prevalence of 2.5 on a 10-point scale was chosen as clinically significant and is consistent with published data.^{22,18,17} Using a standard deviation of 2.9 and a difference in pain scores of 2.5 setting the level of significance, 21 patients are required in each group to provide a power of at least 80% to reject the null hypothesis (H0) that the Anchorsure® System does not lead to significantly less postoperative buttock and posterior thigh pain than does the Capio[™] Slim Device in favor of the alternate hypothesis that the Anchorsure® System leads to significantly less postoperative pain than the Capio[™] Slim Device using a two-sample normal approximation test of means with a two-sided 5% significance level. Assuming a 15% loss to follow-up or drop-out rate for the duration of the study, the total enrollment goal is 48 patients (24 in each group). The null hypothesis will be declared rejected if the mean of immediate postoperative buttock and posterior thigh pain with use of the Anchorsure® device is less from the mean with the use of the Capio[™] Slim device with a p-value of 0.05 or less. The power calculations and their adjustment from the original study goal of 60 recruited patients (using 90% power and a standard deviation of 3) were confirmed with the Wake Forest Baptist Hospital CTSI Biostatistics Department.

Form / Intervention	Preop Clinic	Intra- operatively	Day 1	Week 1	Week 6
Informed Consent	Х				
Study Inclusion Form	Х				
Preop Baseline Data Form with					
Charlson Comorbidity Index and	Х				
POP-Q					
PFDI-20 and PFIQ-7 Forms	Х				Х
NRS Pain Questionnaires	Х		Х	Х	Х
Oral Opioid Use Questionnaire				Х	
Randomization		Х			
Adverse events		Х	Х	Х	Х
Surgeon Questionnaire		Х			

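### Hypothesis 2 predicts similar secondary outcomes, but the plan sets only difference tests and no margin, so its sole support for similarity would be a non-significant p-value

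*Combined protocol and SAP*

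**What the plan says.** Study Objectives, Hypothesis 2, names seven outcomes: surgeon satisfaction, surgical efficiency, intraoperative complications, objective success, symptomatic success, opioid use in the first week after discharge, and pelvic pain. It predicts the same for all of them, ending "overall postoperative pelvic pain will be similar for both devices". It does not define similar.

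The tests are in Post-Intervention Assessments, Clinical outcomes: "Independent t-tests will be used for all continuous data, except for the PFDI and PFIQ data that will use paired t-tests", and "Chi-square tests will be used for all dichotomous and categorical data". No equivalence or non-inferiority margin, interval criterion or power is given for any of the seven. The one threshold, "A clinically significant difference will be considered 2.5 on the 10-point NRS", is set for the primary outcome, buttock or posterior thigh pain. The Power Calculation section covers that outcome alone, using a "two-sample normal approximation test of means with a two-sided 5% significance level".

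Background and Significance says that "improved surgeon efficiency, or decreased operative time with the use of the Anchorsure device will demonstrate an advantage of the suture anchoring devices", and the opening summary says the same. Specific Aim 2 defines efficiency as minutes from first use of the device until the surgeon is satisfied with the sutures. Operative time is not defined as an outcome anywhere.

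**The concern.** A difference test can give evidence that two devices differ. A non-significant result does not give evidence that they are alike unless the interval also excludes differences that matter, and the plan never says which differences those are. With so few patients, p > 0.05 is a common result even when the devices differ substantially.

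Symptomatic success has a further gap. A paired test of PFDI or PFIQ asks whether scores changed after surgery. Both arms could improve significantly by quite different amounts, and the planned tests would not show it.

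At stake is what the report may say about the anchor device on apical success and complications. Appendix 1 gives abstract data on only 13 patients for Anchorsure attached to suture, so a statement that it performs similarly to the standard device would carry weight.

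The efficiency wording adds a smaller problem. The outcome is predicted to be similar, yet a favourable difference on it would be presented as demonstrating an advantage, partly through a measure that is not defined.

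**Working it through.** **Inputs from the documents.** Planned enrolment is 24 per arm with 15% loss, so 24 × 0.85 = 20.4 evaluable; I use 20 to 24 per arm. The SD is 2.9 and the primary difference 2.5 (Power Calculation). Capio Slim success is 92–95% at 17 months (Appendix 1).

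**Assumptions.** The documents give no SD for general pelvic pain, so 2.9 is borrowed from the primary outcome. They give no 6-week success rate, so the 17-month figure stands in. The 93% v 78% scenario and all margins are illustrative.

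**The plan's own figure.** n = 2 × (2.9 × (1.96 + 0.842) / 2.5)² = 21.1 per arm. The stated 21 gives 79.8% power by the normal approximation, so the figure reproduces within rounding. It says nothing about Hypothesis 2.

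**Precision for surgical success.** Half-width = 1.96 × √(2p(1 − p)/n).

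| | n = 20 | n = 24 |
|---|---|---|
| p = 0.92 | 16.8 points | 15.3 points |
| p = 0.95 | 13.5 points | 12.3 points |

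**Precision for pelvic pain.** Half-width = t × 2.9 × √(2/n).
- n = 20: 2.024 × 0.917 = 1.86 points
- n = 24: 2.013 × 0.837 = 1.69 points

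**How often a real difference would be non-significant.**
- Success 93% v 78%, uncorrected chi-square, by enumerating all outcomes: 73% of the time at n = 20 and 67% at n = 24.
- Pelvic pain, t-test, n = 24 to n = 20: a true 1.0-point difference is missed 78–81% of the time, 1.5 points 58–64%, and 2.0 points 35–43%.

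**Could similarity in pelvic pain be shown against a margin M?** Use two one-sided 5% tests with no true difference. Power = 2Φ(M/SE − 1.645) − 1, where SE = 2.9 × √(2/n), or 0.895 at n = 21 and 0.837 at n = 24.

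| Margin | n = 21 | n = 24 |
|---|---|---|
| 1.5 | 2% | 12% |
| 2.0 | 44% | 54% |
| 2.5 | 75% | 82% |

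These tests correspond to a 90% interval inside the margin. Requiring a 95% interval inside 2.5 points lowers the power to about 60% (n = 21) and 70% (n = 24).

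**Could it be shown for success?** Non-inferiority at one-sided 2.5% and 80% power with a 10-point margin needs 2p(1 − p) × (2.802/0.10)² per arm. That is 116 at 92% success and 75 at 95%.

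No such calculation is possible for efficiency: Appendix 1 gives a mean of 6.9 minutes for Capio Slim but no SD.

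**The case against.** The strongest reply is that nothing in the documents says a non-significant result will be read as similarity. The secondary aims are worded as comparisons, the only decision rule concerns pain, and the trial is presented as leading to a larger efficacy study. That is right, and a reader who infers that the sponsor will draw this conclusion goes beyond the text. What stands is narrower: the plan states a hypothesis of similarity and offers no other route to supporting it.

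A reader might also infer that the trial is incapable of showing similarity on anything. For pelvic pain that is too absolute. The interval half-width is smaller than 2.5 points, the only clinically important difference on the scale that the documents give, and power against that margin is reasonable. If the SD were 2.0, 18 per arm would suffice for a 2.0-point margin with one-sided 5% tests. But no margin is stated, and one chosen after the data are seen would not be credible.

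It is tempting to call the efficiency statements a flat contradiction. They are not quite that: one is a prediction, and the other says what a favourable result would mean. They should still be aligned.

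It is also tempting to read the advantage sentence as inflating the false-positive rate. Counting pain, efficiency and operative time as three independent favourable-direction tests gives 1 − 0.975³ = 7.3%. If operative time is loose wording for device minutes, two tests give 1 − 0.975² = 4.9%. Independence is doubtful, and pain itself is measured at three time points. So 5–7% is an illustration and not an error rate of this plan.

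Finally, the success inputs are soft. The reference rate is from 17 months, and the plan describes 6-week failure in two ways: Stage II or greater in Specific Aim 2, and apical descent beyond half the vaginal length under Clinical outcomes.

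**Conclusion.** The concern holds in this form: the planned analysis cannot support Hypothesis 2 as written. There is no margin or interval criterion, and symptomatic success has no between-device test. A non-significant p-value at 20 to 24 per arm would leave differences of about 12–17 percentage points in success, or 1.7–1.9 points in pelvic pain, on either side of the estimate. An assumed true 15-point deficit in success would usually go undetected (67–73%). These sizes rest on the borrowed SD of 2.9 and the 17-month success rate. The missing margin and missing between-arm comparison do not depend on either.

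Similarity in pelvic pain could be shown only against a wide pre-stated margin: about 75–82% power at 2.5 points with 21–24 per arm and one-sided 5% tests. For success, a 10-point margin is out of reach at this size.

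The primary analysis is unaffected. The point should be addressed because it governs what may be concluded about the secondary outcomes.

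**What to change.** - Reword Hypothesis 2 as estimation.
- Under Clinical outcomes, report every secondary outcome as a between-arm difference with a 95% confidence interval. Include the change in PFDI-20 and PFIQ-7 from baseline to 6 weeks, which supplies the missing device comparison.
- State that p > 0.05 will not be read as similarity. Any claim of similarity should require the interval, at a stated level, to lie within a margin fixed before the data are seen.
- In the opening summary and Background and Significance, replace the efficiency and operative-time wording with the device-minutes outcome of Specific Aim 2, described as supportive only.

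This costs wording and a little extra analysis. It needs no new patients, visits or data, because both questionnaires are already scheduled before surgery and at week 6. The downside is that the trial gives up a similarity claim, which the plan as written could not have supported.

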A computer-generated random allocation using a randomly permutated block design (10-patients per block) will be utilized. Randomization will be performed at the start of the study with study group assignments placed in sealed nontransparent envelopes. The envelopes will be numbered in order. The next envelope in numerical order will be brought to the operating room where it will be opened by a participating surgeon and another operating room staff member. Both personnel will sign the envelope to validate that proper envelope opening and interpretation were performed. The envelopes will then be collected for record keeping. This procedure will help to minimize surgeon bias as it is impossible for surgeons to be masked to the randomization. Participants and research staff will be masked during the study as much as possible, however there will be a description of the type of sacrospinous ligament fixation device used within the body of the operative note for each patient that research staff could gain access to. Intraoperative data, including any adverse event that may unmask the study coordinators, will be reported by the surgeon directly to the study administrators.

STUDY INTERVENTION

The primary intervention is sacrospinous fixation utilizing either the Anchorsure® system or the Capio[™] Slim device. Concomitant anterior and/or posterior colporrhaphy (plication of fibromuscular vaginal tissue), enterocele repairs, transvaginal hysterectomy, bilateral salpingo-oophorectomy, perineoplasty, midurethral sling procedures, or other procedures not involving the pelvis, anus, buttock, or lower extremities may be performed. Prolapse procedures will be recorded but not controlled by study protocol. Participating surgeons are all extensively experienced in sacrospinous ligament fixation. Any use of allograft, xenograft, or synthetic graft material for POP repair will not be permitted.

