Access to the retroperitoneal space will be accomplished either via a circumferential pericervical, an anterior, or a posterior. The method of surgical approach will be recorded. Sharp and blunt dissection will be performed to gain access to the sacrospinous ligament(s). Surgeon discretion will determine if unilateral or bilateral fixation is performed for vaginal vault suspension but only unilateral sacrospinous ligament suspension will be permitted for hysteropexy. Surgeon discretion will determine the type and number of sutures or anchors to be placed through the sacrospinous ligament and this data will be recorded. All sutures and anchors placed into the sacrospinous ligament will be placed at least 2cm medial to the ischial spine. Suture(s) will be placed through any anchors with the choice of suture to be determined by the surgeon as this is not anticipated to interfere with any results. The suture(s) placed through anchors or the sacrospinous ligament directly will then be attached to the cervix and/or vaginal apex. Sacrospinous sutures will be tied down once all mid-vaginal repairs are completed. Transvaginal hysterectomy, bilateral salpingectomy, bilateral oophorectomy, and enterocele repair procedures will be performed prior to sacrospinous ligament fixation.

POST-INTERVENTION ASSESSMENTS

The primary study endpoints will be assessed on postoperative day 1, postoperative week 1, and postoperative week 6 via a NRS. Day 1 questionnaires will be given during morning rounds. 1 week following their procedure, patient's will be called at home to remind them to fill out the week 1 questionnaire that would have been given to them during their hospital stay. This questionnaire will be accompanied with a pre-paid and pre-addressed envelope for the patient to use or, if desired, they can bring the completed week 1 questionnaire to their week 6 follow up appointment. All patients will return to the clinic for 1-week and 6-week post-surgery follow up appointments and will fill out an NRS pain assessment (1-week and 6-week), opioid use questionnaire (1-week), PFDI questionnaire (6-week), physical examination including POP-Q (6-week), and review of any postoperative complications (1-week,6-week).

Clinical outcomes

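### Device time ends on the unmasked surgeon's own judgement, yet the summary and background let this secondary outcome alone establish an advantage for Anchorsure

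*Combined protocol and SAP*

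**What the plan says.** Study Objectives, Specific Aim 2, makes surgical efficiency a secondary outcome. It is measured in minutes "from the start of the use of the surgical device until the surgeon is satisfied with the application of all sacrospinous sutures", and tying down is not needed for the clock to stop. No other observable end event is given and no timekeeper is named.

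Randomization and Masking accepts that "it is impossible for surgeons to be masked to the randomization". It also states: "Intraoperative data, including any adverse event that may unmask the study coordinators, will be reported by the surgeon directly to the study administrators". Study Intervention adds a further source of variation in the work being timed: "Surgeon discretion will determine the type and number of sutures or anchors to be placed through the sacrospinous ligament".

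Three parts of the plan bear on what a difference in device time would mean:

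- The opening summary and Background and Significance join less pain, better efficiency and shorter operative time with the word or. The sentence in both places reads in part "improved surgeon efficiency, or decreased operative time with the use of the Anchorsure device will demonstrate an advantage of the suture anchoring devices", and the stated consequence is that this "will fuel the need for a larger efficacy study for the Anchorsure device".
- Hypothesis 2 lists surgical efficiency among the outcomes for which no difference is expected. Its list ends with "overall postoperative pelvic pain will be similar for both devices".
- The Power Calculation declares the null hypothesis rejected on mean immediate postoperative buttock and posterior thigh pain only.

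Clinical outcomes, under Post-Intervention Assessments, treats efficiency as a continuous secondary outcome compared by independent t-test. No multiplicity control is stated for secondary outcomes.

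**The concern.** The clock stops on a judgement made by someone who knows which device is in use. The same surgeon also rates satisfaction with the device, on a questionnaire that the Calendar of Events schedules intraoperatively. A surgeon who favours the new device, or is wary of it, could call the stop slightly earlier or later in one arm without meaning to. Randomisation does not prevent this. The sealed envelope with two signatures protects allocation, not timing.

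For an ordinary secondary outcome this would be a limitation to report. It matters more here because the summary and background make the outcome a sufficient route to a declared advantage and to the case for a larger trial. A systematic timing difference could then support that conclusion with no benefit in pain and no real difference in the work done.

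**Working it through.** **1. The advantage statement against the rest of the plan**

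- Summary and background: improvement in pain, or efficiency, or operative time is enough.
- Hypothesis 2: efficiency is expected to be similar.
- Specific Aim 2 and Clinical outcomes: efficiency is secondary.
- Power Calculation: the only rejection rule is on pain.

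The first is broader than the other three, and they cannot all govern the conclusion. Operative time is also not listed as a separate outcome in Specific Aim 2.

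**2. What the plan sizes**

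The plan gives no sample size or power for device time, so there is no figure on this point to reproduce. The pain calculation (difference 2.5, SD 2.9, two-sided 5%, 80% power) gives 22 per group when recomputed, against 21 stated; power at 21 is 79.8%. It does not depend on device time. The enrolment goal is 48, or 24 per arm.

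**3. Scale of a timing shift**

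Appendix 1 gives 6.9 minutes for the fixation step with Capio Slim, without an SD. An assumed shift of 0.5 to 1 minute is 0.5/6.9 = 7% to 1.0/6.9 = 14% of that time.

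**4. Effect on the t-test**

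Inputs from the plan: independent t-test and 24 per arm. I assume a two-sided 5% level, which the plan states only for the primary outcome, and no loss, since the measure is intraoperative. Also assumed, because the documents do not give them: SD of 2 to 5 minutes, no true difference, and a constant shift b favouring Anchorsure.

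- Standard error = SD × √(2/24) = 0.2887 × SD.
- Critical value with 46 degrees of freedom = 2.013.
- Smallest significant difference = 2.013 × 0.2887 × SD.
- Noncentrality = b / (0.2887 × SD).
- Chance of a significant result favouring Anchorsure = upper tail of the noncentral t beyond 2.013. With b = 0 this is 2.5%.

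| Assumed SD (min) | Smallest significant difference (min) | b = 0.5 min | b = 1 min |
|---|---|---|---|
| 2 | 1.16 | 13.3% | 39.6% |
| 3 | 1.74 | 8.2% | 20.3% |
| 4 | 2.32 | 6.2% | 13.3% |
| 5 | 2.91 | 5.3% | 10.0% |

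The range is about 5% to 40%, against 2.5% without a shift.

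**5. The or rule without any bias**

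Three independent routes, each tested at two-sided 5%, give 1 − 0.95³ = 14.3% for at least one false positive in either direction, and 1 − 0.975³ = 7.3% in favour of the new device. If efficiency and operative time are one measure, the two-route figures are 9.8% and 4.9%. Independence is an assumption, and efficiency and operative time would probably be correlated.

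**The case against.** A reader might infer that the trial can claim success on an end point that the surgeon controls. The documents do not support that. Device time is already labelled secondary, and the only formal rejection rule rests on pain. The advantage sentence stands in the summary and background, not in the analysis text, and what it leads to is a further study. The summary also still gives 60 patients where the Power Calculation gives 48, so it is not the operative text. Nor does the surgeon fully control the time: the stop call and the number of sutures or anchors influence it, but so does the work itself. That the surgeon also holds the clock is an inference from who reports the intraoperative data.

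The size is also open. No shift is documented, its direction is unknown, and opposite leanings among surgeons could partly cancel.

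A stop based on acceptance of the placement has real merit, because it captures replacements and all suture work in both arms. An apparently more objective stop, such as last withdrawal of the device, would still depend on the surgeon's decision to withdraw it. It could also leave out a step: Study Intervention has suture placed through the anchors and does not say whether that happens before or after withdrawal. If after, that clock would favour Anchorsure.

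These points limit the concern and shape the remedy. They do not remove the subjective, unmasked stop, or the conflict between the advantage sentence and the rest of the plan.

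**Conclusion.** The concern holds in a limited form. Surgical efficiency is a secondary outcome open to assessor bias, and the summary and background give it, or operative time, more weight than Hypothesis 2 and the Power Calculation allow. The primary pain test and its sample size are not affected.

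The vulnerability follows from the text; its size does not. The range of about 5% to 40% rests on an assumed SD of 2 to 5 minutes, 24 per arm, no true difference, and an assumed consistent shift of 0.5 to 1 minute in favour of the new device. It shows what a modest shift could do, not what will occur. The change is worth making because it is cheap and removes an internal conflict, not because the trial's main conclusion is at risk.

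**What to change.** 1. In the opening summary and Background and Significance, reserve the statement about demonstrating an advantage for the primary pain comparison. Describe efficiency and operative time as secondary and supportive, in line with Specific Aim 2, Clinical outcomes and the Power Calculation.

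2. Have an operating-room staff member already present write down the start and stop times; one such person already co-signs the envelope. Log the stop when the surgeon announces that the final suture or anchor is accepted, with its suture in place and any replacement included, so that the same work is timed in both arms. Do not use last withdrawal of the device as the stop, because it may omit a step in the anchor arm.

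The cost is two recorded times per case and edits to two sentences, with no change to sample size, technique or patient burden. The trial gives up a stand-alone efficiency claim. The stop call also remains partly the surgeon's judgement: independent logging reduces reporting bias but does not remove the influence of knowing the device, and the report should say so.
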